2. OBJECTIVES

2.1 Primary objective

- To determine whether axitinib given on an individualized dose/schedule for metastatic renal cell carcinoma following immunotherapy with PD-1 and PD-L1 Inhibitors leads to improved PFS.

2.2 Secondary objectives

- To characterize the objective response rates in patients given axitinib on an individualized dose/schedule
- To evaluate the tolerability and safety of an alternative method of axitinib titration.
- To characterize the anti-tumor effect, as measured by change in tumor burden per RECIST 1.1, of axitinib titration performed after initial RECIST PD on axitinib

3. SUBJECT SELECTION

This trial will be conducted in compliance with this protocol and with oversight by our institution's Institutional Review Board (IRB). Any questions about eligibility criteria must be addressed prior to patient registration.

3.1 Inclusion criteria

Patients will be eligible if they meet all of the following criteria at the time of registration:

- Histologically confirmed, locally recurrent or metastatic clear cell renal cell carcinoma
- Has received one prior systemic therapy regimen for mRCC directed against PD-1 and/or PD-L1 which must have been the most recent regimen
 - Prior high-dose interleukin-2 therapy is permitted in addition to anti-PD(L)1 therapy, but is not required

- Prior bevacizumab or VEGF TKI is permitted either in combination with anti-PD(L)1 therapy OR as monotherapy when given PRIOR to anti-PD(L)1 therapy-
 - Prior treatment with combined ipilimumab and nivolumab is permitted
 - Prior axitinib in any setting is not permitted
- A minimum of two weeks since last dose of most recent RCC therapy assuming resolution of clinically significant treatment-related toxicities to grade 1, baseline, or controlled with supportive medications
- Evidence of measurable disease per RECIST 1.1.
- Male or female, age \geq 18 years
- Karnofsky performance status \geq 70 %.
- Adequate organ function as defined by:
 - Absolute neutrophil count (ANC) \geq 1,000/ μ L
 - Platelets \geq 100,000/ μ L
 - Hemoglobin \geq 9.0 g/dL
 - Serum calcium \leq 12.0 mg/dL
 - Serum Creatinine \leq 2.0 x ULN
 - Total serum bilirubin \leq 1.5 x ULN
 - SGOT \leq 2.5 x ULN and SGPT \leq 2.5x ULN
- Signed informed consent and willingness/ability to comply with scheduled visits, treatment plans, laboratory tests, and other study procedures

3.2 Exclusion criteria

Patients will be ineligible if they meet any of the following criteria at the time of registration:

- Non clear cell RCC
- Major surgery within 4 weeks of starting the study treatment.
- Radiation therapy within 2 weeks of starting the study treatment. Prior palliative radiotherapy to metastatic lesion(s) is permitted, provided there is at least one measurable lesion that has not been irradiated.
- NCI CTCAE Version 4.03 grade 3 hemorrhage within 4 weeks of starting the study treatment (Section 15.4).

- Any of the following within the 6 months prior to study drug administration: myocardial infarction, severe/unstable angina, coronary/peripheral artery bypass graft, symptomatic congestive heart failure, cerebrovascular accident or transient ischemic attack.
- Ongoing cardiac dysrhythmias of NCI CTCAE Version 4.03 grade ≥ 2 . Controlled atrial fibrillation is permitted.
- Uncontrolled hypertension ($>160/100$ mm Hg despite optimal medical therapy)
- Concurrent treatment on another clinical trial. Supportive care trials or non-treatment trials, e.g. QOL, and imaging trials, are allowed.
- Pregnancy or breastfeeding. Female subjects must be surgically sterile or be postmenopausal, or must agree to use effective contraception during the period of therapy. All female subjects with reproductive potential must have a negative pregnancy test (serum) prior to enrollment. Male subjects must be surgically sterile or must agree to use effective contraception during the period of therapy. The definition of effective contraception will be based on the judgment of the principal investigator or a designated associate
- Other severe acute or chronic medical or psychiatric condition or laboratory abnormality that may increase the risk associated with study participation or study drug administration, or may interfere with the interpretation of study results, and in the judgment of the investigator would make the subject inappropriate for entry into this study.
- Uncontrolled CNS metastases. Patients are considered to have controlled CNS metastases (and thus eligible) if they have completed local therapy (XRT and/or surgery) and are off steroids with clinical and radiographic stability 1 month from the end of CNS-directed therapy.

4. STUDY CALENDAR

Required Investigations	Baseline (within 4 weeks prior to C1D1)	First Cycle (28 days)		Day 7 and 14 after each dose change (+/- 2 working days)	Each Cycle Day 1^{3,5} (28 days +/- 3 working days)	Safety assessment⁶ (Within 30 days after off treatment +/- 3 days)
		Day 7¹ (+/- 2 working days)	Day 14¹ (+/- 2 working days)			
History and Physical Exam	X				X ⁹	
KPS and ECOG performance status	X				X	
Informed consent	X					
Assessment of Toxicity		X (phone call)	X (phone call)	X (phone call and/or clinic visit)	X	Assess for resolution of treatment-related toxicities within 30 days of last dose
CBC w/ differential, CMP, and LDH⁷	X				X	as clinically indicated
TSH, T3, T4	X				X ⁴	as clinically indicated
Pregnancy Test⁸	X					
EKG	X					
Radiographic Assessment²	X				X ⁵	
Patient diary (BP/dosing)	X-----X					

1 No dose escalation prior to day 14 of cycle 1

2 CTs (head, chest, abdomen, pelvis; with oral and IV contrast if possible) and bone scan required at baseline and must be done within 28 days of registration. MRI is allowed instead of CT head at baseline.. CT head will be done after baseline as clinically indicated. Follow-up scans are based on C1D1 date regardless of the date of baseline scans.

3 Beginning at C5D1 this column can be extended to every 2 cycles per provider discretion. Following C13D1 visit, this can be extended to every 12 weeks (i.e., 3 cycles)

4 Tests to be done at imaging timepoints

5 After baseline, bone scan only if indicative of metastatic disease at baseline or if clinical signs/symptoms develop. CT Chest-Abdomen-Pelvis will be done every 8 weeks based on C1D1 date regardless of the date of baseline scans. Following Cycle 13 Day 1 assessment, CT scans to be done every 12 weeks. [Note: patients continuing axitinib post-PD will have CT c/a/p every 8 weeks and bone scans as needed per MD discretion]

Following Cycle 7 Day 1 disease assessment, bone scan to be done every 16 weeks per MD discretion (and every 24 weeks after C13 per MD discretion)

6 Treatment-related AE reporting ends at the time new treatment is started (see section 9.6). After C13D1, all SAEs will be documented, AEs will be followed per SOC but not necessary to document for study-related purposes.

7 LDH at baseline only

8 Serum pregnancy test for women of childbearing potential. No childbearing potential defined as > 12 months of non-therapy-induced amenorrhea or surgically sterile.

9 Targeted physical exam per MD discretion when patient is in for a clinic visit
 Protocol treatment should begin within 3 working days of patient registration.

5. DOSE-TITRATION SCHEMA

Dose Level	Dose	If grade 2 or greater toxicity during days 1-7 ^a	If grade 2 or greater toxicity during days 8-14 ^a	If no grade 2 or greater toxicity after 14 days ^a
Dose reduction level 3	2 mg BID	Discuss with study sponsor	Hold axitinib if needed (e.g. 3 days) then resume at 2 mg BID with breaks as needed ^c	Stay on 2mg BID ^c
Dose reduction level 2	3 mg BID	Dose reduce to 2mg BID ^b (can hold axitinib prior to restarting per MD discretion)	Hold axitinib if needed (e.g. 3 days) then resume at 3 mg BID with breaks as needed ^c	Stay on 3mg BID ^c
Dose reduction level 1	4 mg BID	Dose reduce to 3mg BID ^b (can hold axitinib prior to restarting per MD discretion)	Hold axitinib if needed (e.g. 3 days) then resume at 4 mg BID with breaks as needed ^c	Stay on 4mg BID ^c
Starting dose level	5 mg BID	Dose reduce to 4mg BID^b (can hold axitinib prior to restarting per MD discretion)	Hold axitinib if needed (e.g. 3 days) then resume at 5 mg BID with breaks as needed^c	Dose escalate to 6 mg BID
Dose escalation level 1	6 mg BID	Dose reduce to 5mg BID ^b (can hold axitinib prior to restarting per MD discretion)	Hold axitinib if needed (e.g. 3 days) then resume at 6 mg BID with breaks as needed ^c	Dose escalate to 7 mg BID
Dose escalation level 2	7 mg BID	Dose reduce to 6mg BID ^b (can hold axitinib prior to restarting per MD discretion)	Hold axitinib if needed (e.g. 3 days) then resume at 7 mg BID with breaks as needed ^c	Dose escalate to 8 mg BID
Dose escalation level 3	8 mg BID	Dose reduce to 7mg BID ^b (can hold axitinib prior to restarting per MD discretion)	Hold axitinib if needed (e.g. 3 days) then resume at 8 mg BID with breaks as needed ^c	Dose escalate to 10 mg BID ^d
Dose escalation level 4	10 mg BID	Dose reduce to 8mg BID ^b (can hold axitinib prior to restarting per MD discretion)	Hold axitinib if needed (e.g. 3 days) then resume at 10 mg BID with breaks as needed ^c	Discuss dose escalation with sponsor

^a Dosing modifications based only on the following grade 2 toxicities: oral mucositis, diarrhea, hand-foot syndrome, fatigue. Dose modifications for other axitinib-related AEs can be considered per study principal investigator.CTC v4 definitions of grade 2 toxicities:

Oral mucositis: Moderate pain; not interfering with oral intake; modified diet indicated

Diarrhea: Increase of 4 - 6 stools per day over baseline

HFS: Skin changes (e.g., peeling, blisters, bleeding, edema, or hyperkeratosis) with pain; limiting instrumental ADL

Fatigue: Fatigue not relieved by rest; limiting instrumental ADL

^b After dose reduction, re-escalation as tolerated may be considered per provider discretion

^c Give break if needed (e.g. 3 days) when grade 2 or greater mucositis, diarrhea, HFS or fatigue develops. If patient consistently develops grade 2 or greater toxicity within 7 days on therapy after a break, consider dose reducing by one level

^d Dose escalation to 9mg BID can be considered per provider discretion

6. TREATMENT PLAN

This prospective single arm study will evaluate the efficacy and safety of axitinib given on an individualized dosing schedule in subjects with metastatic clear cell RCC who have been treated with PD-1 and PD-L1 inhibitors. All subjects will be followed for Progression Free Survival (PFS), including patients who discontinue axitinib for toxicity.

6.1 Treatment schedule

The intent is to maximize sustained dose intensity of axitinib based on individual tolerability using the dose modification criteria described in Section 5. Dose and schedule changes are done if specific toxicity (oral mucositis, diarrhea, hand-foot syndrome, fatigue) is \geq grade 2. Patients will initially continue therapy until progression according to RECIST criteria version 1.1 (Section 15.1). At progressive disease dose escalation above current dose is allowed based on investigator discretion of clinical benefit. However, axitinib should be discontinued if a second RECIST PD following dose escalation, patient intolerance, or at provider discretion.

6.2 Subject compliance and dropout

Patients must strictly follow the dosing schedule during each course as described by their treating investigator. Compliance to study medication and blood pressure records will be ascertained by use of patient diaries and pill count (Section 15.5). Patients will record the date, time and number of pills consumed in the diary on a daily basis. The patient diary should be reviewed with the patient for completion and to address any discrepancies or absent data. The principal investigator or the designee will account for the number of capsules dispensed against those returned by the subject. Any deviations and missed doses will be recorded in the CRF and drug accountability logs for verification with the reasons.

The investigator/designee will try to ensure complete compliance with the dosing schedule by providing timely instructions to the subjects. Patients withdrawn prior to completion of first course because of non-compliance not related to study drug related toxicity will be replaced. **Completed diary sheets must be submitted to CCF.**

6.3 Premature withdrawal/ discontinuation criteria

Patients may withdraw from the trial at any time, for any reason, at their own request.

Patients may be withdrawn at any time at the discretion of the investigator or sponsor for concurrent illness, safety, behavioral, or other reasons.

If a patient does not return for a scheduled visit, every effort should be made to contact the patient. In any circumstance, every effort should be made to document patient outcome and reason for withdrawal, if possible. The investigator should request the patient return all unused investigational product(s), request the patient to return for a final visit, if applicable and follow-up with the subject regarding any unresolved adverse events.

If the subject withdraws from the trial and also withdraws consent for disclosure of future information, no further evaluations should be performed and no additional data should be collected. The sponsor may retain and continue to use any data collected before such withdrawal of consent.

Patients will be withdrawn from treatment in the case of:

- Disease progression per RECIST v1.1. **Patients with initial disease progression are permitted and encouraged to stay on therapy with further axitinib upward dose titration (following the dose titration schema in Section 5) at MD discretion of clinical benefit until a second RECIST v1.1 PD.** Principal Investigator ([name] MD) & Cleveland Clinic Data Manager must be notified by email when a patient with disease progression will be continuing on study for clinical benefit.
- Unacceptable toxicity
- Need for anti-cancer therapy not specified in the protocol. Surgery to remove a metastasis or palliative radiotherapy is permitted after discussion with the Principal Investigator ([name]).

- Patient noncompliance
- Patient lost to follow-up
- Patient choice to withdraw from treatment (follow-up permitted by patient)
- Patient choice to withdrawal consent to study (cessation of follow-up)

6.4 Concomitant Medications

The following medications/classes taken during the 15 days prior to Cycle 1 Day 1 and through Cycle 13 Day 1 must be recorded on the CRF.

- a. All cardiac medications**
- b. CYP3A4 meds (specifically omeprazole, pantoprazole, lansoprazole, rabeprazole, esomeprazole, dexamethasone, diltiazem, phenytoin, rifampin, St. Johns wort, carbamazepine, phenobarbatol, amobarbitol, primidone, rifabutin, felbamate, verapamil, grapefruit juice, ketoconazole, itraconazole, erythromycin, clarithromycin, indinavir, saquinavir, ritonavir, nelfinavir, lopinavir, amprenavir, delavirdine and nefazodone)**
- c. Steroids (include dose)**
- d. Anti-diarrheals**

6.4.1 Inhibitors and Inducers of CYP3A4

Axitinib is primarily metabolized in the liver by CYP3A4/5.²² There was a 1.5- and 2-fold in C max and AUC ∞ , respectively when axitinib was co-administered with ketoconazole, a potent inhibitor of CYP3A4. Similarly, the C max and AUC ∞ decreased 71% and 79%, respectively when co-administration of rifampin, a strong CYP3A4/5 inducer. Therefore, co-administration with potent inhibitors (ketoconazole, itraconazole, clarithromycin, diltiazem, delavirdine, indinavir, saquinavir, ritonavir, atazanavir, nelfinavir) and strong inducers (rifampin, rifabutin, carbamazepine, phenobarbital, phenytoin, St. John's wort, efavirenz, tipranavir) of CYP3A4 may result in significant increases/decreases in exposure of axitinib and may alter the safety/efficacy of the drug.

During the study, concurrent administration of potent CYP3A4 inhibitors and inducers (omeprazole, pantoprazole, lansoprazole, rabeprazole, esomeprazole, dexamethasone, diltiazem, phenytoin, rifampin, St. Johns wort, carbamazepine, phenobarbital, amobarbital, primidone, rifabutin, felbamate, verapamil, grapefruit juice, ketoconazole, itraconazole, erythromycin, clarithromycin, indinavir, saquinavir, ritonavir, nelfinavir, lopinavir, amprenavir, delavirdine and nefazodone) are not recommended.

Alternative therapies should be used when available.

6.4.2 Anticoagulants

The use of Coumarin-derivative anticoagulants such as warfarin (Coumadin) is not recommended.

6.4.3 Other Anticancer or Experimental Therapy

No other approved or investigational anticancer treatment will be permitted during the study period, including chemotherapy, biological response modifiers, hormone therapy, or immunotherapy. No other investigational drug may be used during treatment on this protocol, and concurrent participation in another clinical trial is not allowed. Supportive care trials or non-treatment trials, eg. QOL, and imaging trials are allowed.

6.4.4 Antiemetic and Antidiarrheal Therapy

Supportive care may include premedication with antiemetics to limit treatment-related nausea and vomiting. Patients may receive prophylaxis of treatment-induced diarrhea.

6.4.5 Hematopoietic Growth Factors

Prophylactic use of hematopoietic growth factors to support neutrophil or platelet counts is not permitted during this study. Patients who enter the study on stable doses of erythropoietin or darbepoietin may continue this treatment, and patients may start either drug during the study at the discretion of the investigator. Patients with neutropenic fever or infection should be treated promptly and may receive therapeutic colony-stimulating factors if appropriate.

6.4.6 Other Concomitant Medications

Anti-inflammatory drugs should be avoided to preserve renal function but narcotic analgesics may be offered as needed. Packed red blood cell and platelet transfusions should be administered as clinically indicated.

Patients on this trial may be supported with appropriate hormone replacement therapy in the event they develop adrenal insufficiency in the absence of disease progression or unacceptable treatment-associated toxicity. Patients may receive bisphosphonates or denosumab for treatment of their bone metastases or hypercalcemia.

6.4.7 Concomitant Radiotherapy or Surgery

Palliative radiotherapy to specific sites of disease is permitted if considered medically necessary by the treating physician. Patients requiring radiotherapy will be considered to have disease progression, but may continue on axitinib if felt to be of clinical benefit per MD discretion. Axitinib treatment can continue during simple local radiation to metastatic bone lesions or briefly held at MD discretion. Axitinib should be held during radiotherapy that involves brain and spinal cord. The intensities, number, and dates of doses received for allowed palliative radiotherapy should be recorded on the appropriate CRFs.

6.5 Duration of follow-up

Patients will be followed until they are removed from the clinical trial either due to progressive disease (PD) or other reasons as outlined in section 6.3. A subsequent safety assessment within 30 days (+/- 3 days) will be conducted as per study calendar in section 4. Duration of follow up of AEs and SAEs is listed in section 9.6.

Patients on therapy for more at least 12 months will only be followed for SAEs, imaging, tumor measurements, off-study date, and survival status.

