8.2 Efficacy assessments

Patients must have measurable disease at screening and will be evaluated for response on the basis of RECIST criteria version 1.1 (Section 15.1). Tumor measurements using physical examination, spiral CT scan and/or MRI or other appropriate techniques deemed suitable by the investigator will be performed at screening within 28 days of patient registration and repeated every 8 weeks until disease progression. After baseline, bone scan only if indicative of metastatic disease at baseline or if clinical signs/symptoms develop. CT Chest-Abdomen-Pelvis will be done every 8 weeks based on C1D1 date regardless of the date of baseline scans. Following Cycle 13 Day 1 assessment, CT scans to be done every 12 weeks. Disease assessment with CT chest-abdomen-pelvis will continue every 8 weeks for patients continuing on treatment following disease progression (bone scans to be done per MD discretion). Scans can be done more frequently per MD discretion; these scans will be submitted on an unscheduled disease assessment CRF.

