10. STATISTICAL ANALYSIS

10.1 Study design and justification for sample size

Study design: This is a single-arm, single-stage phase II study investigating the use of an individualized dosing regimen of axitinib in patients with metastatic renal cell carcinoma. The primary outcome for this study is progression-free survival (PFS), defined as the interval between the date a patient first receives axitinib and the date of death or confirmed progression according to RECIST criteria. Any patient alive and without known progression at the time of analysis will be censored as of the last date the patient can be confirmed to be progression-free. Secondary endpoints include overall survival, RECIST-based response, and adverse events defined and graded according to NCI CTCAE Version 4.03 criteria.

Sample size: 38 evaluable patients.

Justification for sample size: Based on prior studies patients treated with axitinib following anti PD-1 therapy for mRCC have a PFS of approximately 6.5 months.^{19, 20} The hypothesis of this study is that with appropriate dose titration based on toxicities patients will reach a more optimal drug dose to increase benefit while minimizing risk. As such, we anticipate an approximately 45% increase in median PFS from 6.5 months to 9.5 months, which is felt to represent a clinically-meaningful improvement. Assuming accrual is fairly

uniform and will take approximately 18-24 months, there will be a minimum of 12 additional months of follow-up once the last patient has entered, and that PFS follows an exponential distribution (which is reasonable based on what has been seen historically in advanced RCC), 38 eligible and evaluable patients will be needed to test the above hypothesis with $\geq 80\%$ power (based on a 1-sided MLE test with 10% type I error). Allowing for ineligible/unevaluable a total of 40 patients will be accrued.

A 20% rate of discontinuation due to toxicity will be considered unacceptable. If at any time $>2/10$, $>4/20$, or $>6/30$ patients need to be discontinued due to toxicity, consideration will be given to stopping the study. With these guidelines the likelihood of a boundary being crossed in the first 10 patients is 7% if the underlying risk is 10%, 32% if it is 20%, and 62% if the risk is 30%. The overall likelihoods of a boundary being crossed at some point are 10%, 53%, and 89%, respectively.

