10.3 Statistical Analysis

Data analysis will primarily be descriptive in nature, although as discussed above the underlying hypothesis that axitinib titration can improve PFS will be tested using a MLE test. Categorical data, such as adverse events and response rate, will be summarized using proportions and frequencies. Continuous endpoints, such as dose information will be summarized using medians and ranges, and PFS and overall survival will be summarized using the Kaplan-Meier method.

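### Section 6.5 ends follow-up at any treatment stop, against Section 6's rule to follow toxicity stops for PFS, and overall survival has no collection schedule

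*Combined protocol and SAP*

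**What the plan says.** **End of follow-up.** Section 6.5 states: "Patients will be followed until they are removed from the clinical trial either due to progressive disease (PD) or other reasons". It refers to Section 6.3 for those reasons and then provides a single safety assessment. The itemised list in 6.3 is introduced as reasons for withdrawal from treatment. It includes unacceptable toxicity, and it separates a patient who stops treatment but allows follow-up from one who withdraws consent, for whom follow-up ceases.

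**PFS follow-up.** Section 6 states: "All subjects will be followed for Progression Free Survival (PFS), including patients who discontinue axitinib for toxicity". Section 8.2 has tumour measurements "repeated every 8 weeks until disease progression". The only post-treatment column in the Section 4 calendar is the safety assessment, "Within 30 days after off treatment +/- 3 days". Section 10.1 censors a patient without known progression at the last date confirmed progression-free. For the sample size it assumes "there will be a minimum of 12 additional months of follow-up once the last patient has entered".

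**Overall survival.** Section 10.1: "Secondary endpoints include overall survival, RECIST-based response, and adverse events". Section 10.3: "PFS and overall survival will be summarized using the Kaplan-Meier method". OS is not among the Section 2.2 objectives. Survival status is named once, in 6.5, for patients on therapy at least 12 months, with no interval, method or end date. The calendar has no survival row.

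**The concern.** Section 6.5 turns a list of reasons for stopping treatment into a list of reasons for ending follow-up. A site that relies on 6.5 and the calendar would stop imaging a patient who comes off axitinib for toxicity. The Section 10.1 rule would then censor that patient at the last progression-free scan. PFS is the only primary endpoint and the intervention is toxicity-driven dosing, so toxicity stops should not be left ambiguous. Events are lost in every case. If patients who stop do worse afterwards, PFS is also overstated.

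For OS, a patient who leaves at progression would be censored about a month after the last dose, when the risk of death is typically rising. That censoring is informative and biases the Kaplan-Meier curve upwards.

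**Working it through.** **1. Reproduce the design (Section 10.1).** Inputs: median PFS 6.5 versus 9.5 months, exponential; one-sided 10% MLE test; n = 38; uniform accrual A = 18–24 months; F = 12 further months.

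- Hazards: λ0 = ln2/6.5 = 0.1066; λ1 = ln2/9.5 = 0.0730; ln(λ0/λ1) = 0.3795.
- P(event) = 1 − [exp(−λF) − exp(−λ(A+F))]/(λA).
- A = 18: d1 = 38 × 0.768 = 29.2 events at the alternative; d0 = 38 × 0.876 = 33.3 at the null.
- Power = Φ{[0.3795 − 1.2816/√d0] × √d1} = Φ{(0.3795 − 0.2221) × 5.403} = Φ(0.850) = 80.2%.
- A = 24: d1 = 30.5, d0 = 34.2, power 81.2%.

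The required n is 38 at A = 18 and 37 at A = 24, so the plan's figure reproduces. Using the alternative variance in the critical value gives 77.9–79.3%.

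**2. Censor at the toxicity stop.** Let a fraction p stop before a PFS event at the 9.5-month median. The competing rate is c = λ1·p/(1−p), and P(event) becomes λ/(λ+c) times the expression above with λ+c in place of λ. The rates 10% and 20% are among those that 10.1 tabulates for toxicity discontinuation. Example, p = 20%, A = 18: c = 0.0182, d1 = 25.4, d0 = 29.6, power = Φ{(0.3795 − 0.2357) × 5.040} = 76.6%.

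| Toxicity stops | Events at 9.5 months | Power, null variance | Power, alternative variance |
|---|---|---|---|
| 0% | 29.2–30.5 | 80.2–81.2% | 77.9–79.3% |
| 10% | 27.4–28.5 | 78.6–79.4% | 76.0–77.2% |
| 20% | 25.4–26.3 | 76.6–77.3% | 73.6–74.7% |

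**3. Type I error, censoring at the stop.** By simulation (60,000 trials per cell), with the overall PFS median, on and off drug together, held at 6.5 months. The hazard ratios after stopping are assumptions. Ranges cover both accrual lengths and both variance forms.

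| Hazard after stopping | 10% stops | 20% stops |
|---|---|---|
| unchanged | 9–10% | 9–10% |
| ×1.5 | 10–11% | 12–13% |
| ×2 | 12–13% | 15–17% |

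With the hazard doubled, a true 6.5-month median would read about 6.7 months (10% stops) or 6.9 months (20% stops). With full follow-up, the ×1.5 and ×2 scenarios give 5–8%, because PFS is then no longer exponential. The comparison is therefore with the planned 10%.

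The result depends on what is held at 6.5 months. If it is the on-drug median (20% stops, hazard doubled), the rejection rate is about 9% with censoring and 3.5% with full follow-up. In that case the overall median is below 6.5 months, and full follow-up reads about 6.0. Either way, censoring gives the more favourable PFS.

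**4. Overall survival.** Under the exponential model, the share free of a PFS event at 12 months is exp(−λ × 12): 28% at a 6.5-month median and 42% at 9.5. Unless they continue axitinib after progression, 58–72% of patients would therefore be off therapy before the only point at which 6.5 names survival status.

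The simulation (400,000 patients per cell) ends survival follow-up one month after the last dose unless total time on therapy reaches 12 months. Assumed: PFS median 9.5 months; 5–20% of PFS events are deaths; median survival after progression 9–18 months. Post-progression therapy has a median of 6.3 months, the figure Section 1.4 cites from a retrospective review.

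| Continue axitinib after PD (assumed) | Deaths captured | 24-month OS overstated by |
|---|---|---|
| 0% | 30–52% | 9–23 points |
| 50% | 52–66% | 5–13 points |
| 80% | 65–75% | 3–8 points |

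**The case against.** The strongest reply is that the plan already answers the PFS question. Section 6 is specific to toxicity stops, 8.2 images until progression, the calendar footnotes tie scans to the first day of cycle 1, and 6.5 speaks of removal from the trial, which need not mean withdrawal from treatment. This is why the bias is only a risk. The conflict remains, because 6.5 points to 6.3, whose itemised list concerns treatment, attaches no follow-up note to toxicity, and has no companion list of off-study reasons in the text available.

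The 12 months in 10.1 can be read as the timing of the analysis and not as a promise to each patient. That is fair, and the contradiction does not rest on it.

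The 12-month sentence in 6.5 may be meant to cut data collection after a year, which would imply that survival status was collected all along. Even so, nothing provides for survival follow-up after removal. The reading does make the OS figures conditional, and their width shows that the size is not known.

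The 20% rate is the one 10.1 calls unacceptable, with a 53% chance of crossing a toxicity boundary, so it is a stress case. The power loss is modest, and an unchanged hazard produces no bias. Both points stand.

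Continued imaging after a non-PD stop also raises the question of patients who start another anticancer therapy before progression. Section 10.1 has no rule for them. That gap exists already, and the amended text is a good place to close it.

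**Conclusion.** The contradiction is real and should be fixed: 6.5 as written conflicts with Sections 6 and 8.2, and OS is to be analysed without a way to collect it. All the sizes apply only if 6.5 is followed literally.

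For PFS, the loss is about 2 to 4 events and 2 to 4 points of power at 10–20% toxicity stops. Type I error rises above the planned 10% only if the hazard increases after stopping, reaching 15–17% at 20% stops with an assumed doubling. For OS, the direction of bias is upwards. Its size, 3 to 23 points at 24 months, rests on assumed inputs. OS is descriptive and drives no decision. The calculation behind 38 patients is sound provided PFS follow-up runs as Section 6 says.

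**What to change.** - **PFS.** In 6.5, state that patients who stop axitinib without RECIST progression keep the existing tumour-assessment schedule until progression, death or data cut-off, unless they withdraw consent to follow-up. Add a matching calendar column. In the same edit, say how PFS is handled if another anticancer therapy starts first.
- **OS.** Either collect survival status for all treated patients by phone or chart, for example about every 12 weeks until 12 months after the last patient enters, or delete OS from 10.1 and 10.3. If it is kept, add it to the Section 2.2 objectives.

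The cost is a few sentences and one calendar column. No imaging is added beyond what Sections 6 and 8.2 already require. Survival checks cover about 40 patients, and deleting OS costs nothing.
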